#### **Recruitment:**

We will contact patients and healthy subjects by phone or/and email by following recruitment phone and email scripts. We will introduce ourselves and introduce the study and ask participants if they are still interested in participating in the study. We are likely to call the parents of patients with autism to ask them if their son is interested in participating given that some patients don't like to be in touch by phone and don't respond to emails. In some cases, we need to call parents who have legal guardianship in order to see if they would be available to accompany or willing to mail us a signed consent form so that their son can participate in the study.

In some cases, we will try to do the recruitment, screening and scheduling in the same phone call.

#### **Screening:**

**The medical screening form (that includes inclusion and exclusion criteria) will be first reviewed over the phone for both healthy subjects and ASD (following an oral consent for screening). In case there is any doubt in the results, the research staff will contact the PI or study physician to make sure that the person can be included in the study. For this initial screening, we do not require study physician signature to enroll a patient in the study. During the research visit, the participant will be asked to review it and sign his name on the form. The legal guardian, if applicable, will be also asked to sign it. The nurse practitioner or the MD need to sign the form also.**

**The MRI screening form will be also reviewed over the phone with the participant (or with the parent of the patient in case it's difficult for the patient to have the discussion over the**

phone) following an oral consent. In case there is a doubt in any of the points, we will ask the MRI specialist to see if we can still include the subject in the study. During the research visit, the participant will review it and sign it and we will give a copy to the MRI technician. The legal guardian, if applicable, will also be asked to sign it.

#### **ASD**

Over the phone, the staff member will go through the oral consent for screening for eligibility. Over the phone, we will conduct the medical screening in order to assess eligibility (as based on the inclusion and exclusion criteria of the study). We will introduce the study and answer any questions about the content of the study. We will also go through the MRI screening in order to assess safety and eligibility. We can send them the MRI screening form by email to review. We will ask participants if they have a legal guardianship. We will document in a screening log who conducted the discussion over the phone, whether the person is eligible, whether there are questions for the PI or MD investigators, and the dates of the phone interview. We will follow a screening phone script to contact patients. It is very likely that we need to contact patients several times in order to finish the screening or to come back to patients about eligibility (in case there were questions to the PI).

In some cases, we need to contact the parents of patients to schedule patients' visits given that the parents are managing their son's schedule, or that it's difficult to reach patients (by email or phone) or that it's difficult for patients to understand instructions over the phone or by email. In these cases, we will need to conduct the interview with the parent. We will go through the same phone script for recruitment and screening that includes an oral consent and eligibility criteria and screening assessment (same phone script as above). We will ask parents to inform the patient about all the details of this interview and ask them if they are interested in participating in the study. We will document that the interview was done with the parent and not with the patient in the screening log documentation. When patients show up for their first visit, we will make sure to go over the eligibility and screening forms again. We will follow-up with the parent and patient by email or phone to schedule all the visits and to confirm appointments.

It is also possible that we do the same phone screener with both parents and patients in case there are some doubts about some answers.

In addition to the phone interview, it is likely that we send the parents and/or patients the MRI screening form via email to go over it in order to double check all the criteria. We will use an email recruitment template.

We will respond to emails and phone calls of parents and patients who have questions or need more information about the study.

For adults who have legal guardianship or legal authority representative, parents need to sign the consent form also (in addition to the adult subject's signature). The parent needs to be present during the first visit and is not required to stay for the rest of the visits. However, we are not asking the permission from the legal guardian to conduct the phone screening process. The LAR will be asked to sign the screening form. We will conduct a parent phone call by following a LAR phone

parent script. We will contact the parent by phone and ask them first to verbally confirm if they have the authority to make research decisions (power of attorney, legal guardianship). Once confirmed, we will introduce the study briefly and ask them if they can accompany their sons for the first research visit. We will explain to them that we need their signature on the consent form in order for their son to participate in the study. In this case, the parent and the patient will sign and date the consent form, as well as the screening forms, during the first research visit. During the research visit, the staff member will discuss the consent form with both patient and parent, and will ask them to read it, to ask questions and to sign it when they are ready. The staff member will provide a copy of the consent to the patient and to the parent. There is no need for parents to accompany their sons for all the visits.

If the parent cannot accompany their son to the research visit (onsite at Emory), we will ask the parent (during the phone interview) if we can mail them the consent form and we will ask them for the mailing address. We will discuss the consent form over the phone. We will let them know that they cannot scan and email us back the consent form. They have to mail the signed consent form back to us to the address [name]. We will mail a copy of the consent form to the parent (one for them to keep as a copy and one for them to sign and send it back to us by mail) and the screening form with a returned envelop (and a stamp) and ask parents to read and sign. We will make sure to have colorful post-it on the pages where the parent needs to sign, date and time. We will ask them to email us or call us in case they have a question. We will make sure that we receive the signed consent form and screening forms from the parent before patient's first research scheduled visit. If the form was not dated or timed correctly or if the parent forgot to add date and/or time, we will write a note to file regarding this event describing the omission of the date and time. We will go ahead and mail again the form to the parent (with the return envelope and a stamp) and ask them to add the date or/and time. The same applies for signature omission or if the signature is misplaced. We will call them or email them to let them know that we are mailing them the consent because of the omission. Once the consent is signed by the experimenter and the patient, we will send a signed copy to the parent by mail or we send 2 signed copies of the consent with the patient (one for the parent).

We will follow a legal guardian phone script while making this phone interview with the legal guardian. We will document who discussed with the parent and what was the content of the discussion in the screening log document.

All the informed consent process with LAR will be documented in the informed consent process note and will be added to subject's individual folder.

We will respond to email requests and phone calls for information with form recruitment email, including available times, documentation and screening form attached if necessary.

If the patient is eligible for the study, we will request an appointment with the CRN and put an appointment in the calendar. We will also reserve the MRI scanner.

Once the CRN approves, we will notify the patient with a reminder email, we will notify [name] or [name] and notify IDS.

### **Healthy subjects screening:**

Given that the healthy group of males should match patients with ASD on age, sex and intellectual quotient (IQ), we will first contact patients (from the data base of the previous protocol 64623) and see who is interested and eligible before selecting the matching healthy men controls. We will select healthy participants who already participated in our previous research study (64623). We will use the information collected in project #64623 to match their IQ and age. We will contact participants who agreed to be contacted in the future studies in the consent form of protocol 64623. We will contact healthy subjects by phone and/or email (again from the data base of 64623) to see if they would be interested to participate and whether they are eligible (based on eligibility criteria for healthy subjects and based on safety screening). We will follow a phone script and email for recruitment for healthy subjects. We will respond to email requests for info and include screening form attached.

Given that mid-way study, we have trouble bringing back healthy participants who have participated previously in protocol 64623, we need to recruit new people from general population in Atlanta. We will use flyers to recruit more people. We will post these flyers in different locations around Atlanta area (like in restaurants, college, Marta stations etc). We will need to conduct the IQ test and color blindness prior their main visit to the hospital. Healthy controls should match ASD patients with IQ and race. We are adding race so that samples from both groups stay matched as much as possible.

We have already conducted the total number of patients for this study. The average IQ of ASD patients is 98.39 and the standard deviation is 16.28. The race ratio for ASD is 82% white, 12.5% African American and 6% more than one race,

Accordingly, we are adding a new informed consent and another inclusion criterion for this separate group of healthy subjects (labeled II). The inclusion criteria will include Caucasian race and IQ range between 70 and 115.

The reason that we are adding Caucasian to the inclusion criteria for this new set of healthy subjects is that we have already 2 or 3 contacts from the previous study who are African American and who are interested to participate. This will make approximately 10% of the healthy subject's sample if we were able to recruit 30 total.

If the IQ was higher or lower than this range, we will exclude the participant from participating in the study. For this new set of healthy subjects, they need to come for 2 separate visits. The first visit will consist of performing the IQ (at the hospital or at [name]) test and consent signature as well as review of eligibility criteria and color blindness test. The second visit will consist of the main clinical visit at the Hospital

If the subject is eligible for the study, we will request an appointment with the CRN and put an appointment in the calendar.

Once the CRN approves, we will notify the subject with a reminder email, we will notify [name] or [name] and notify IDS.

For both healthy subjects and ASD subjects, in case there is any doubt in the screening form or eligibility of participants, prior scheduling the research visit, the PI will be notified and will review the screening form and if needed consult with study physician or study nurse practitioner. If it is determined that the subject meets inclusion/exclusion criteria, the research staff will schedule the different visits of the subject. On the day of the scheduled visit, the study staff will review the consent form with the subject and give them the opportunity to ask any questions before asking them to sign in person.

Subjects will meet the study staff at the entrance of the Emory Hospital.

Patients will participate in 5 visits total and these visits can be separated by a one-week interval approximately ( $\pm$  2 to 3 days). We have to be little flexible in the schedule given that we are dealing with complicated scheduling system (scheduling CRN units at the hospital, MRI scanner at BITC, nurse practitioner or physician, patients' availability).

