Following resting state, participants will perform an emotional face task that consists of looking at morphed faces. We will record eye-movements (via an eye tracker) while participants are looking into faces. Participants will also perform a social ball game (adapted version from our previous project IRB00064623) during which they interact with several other players. Participants will also play a prisoner dilemma game that was previously used by [name]'s work (investigator at Emory) to look into neural correlates of reciprocal cooperation and defect.

Following the scanner, participants will perform some behavioral task and complete some questionnaire in order to study OXT' effects on behavior (such as emotion recognition and alexithymia).

*Social reward and social saliency* are key phenomena for studying the core deficit of social dysfunction in ASD and for targeting oxytocin manipulation.

We are looking into the effects of IN-OT on brain activity and behavior in a precision medicine fashion. As exploratory analysis, we will look into the different clinical, behavioral and genetic moderators that can moderate the effects of IN-OT on behavior.

The major hypothesis of this project is that intranasal oxytocin affects the activity of brain regions and brain connectivity between areas that are involved in sensory and emotional processing as well as interoceptive networks.

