### Clinical Trial

#### 1- Screening and recruitment

All information collected during phone and email correspondences will be documented in an excel sheet on a HIPPA protected location (such as Emory box).

Subjects or and families (healthy subjects and subjects with ASD) will be contacted by email and/or by phone. We are recruiting participants who have previously participated in another study (IRB protocol #64623, where [name] is an investigator) and who agreed to be contacted for future studies or agreed to participate in this study and who have the basic criteria to be eligible for the study (such as IQ>70 and autism diagnosis as based on ADOS and ADI criteria). Contact information will be collected from protocol 64623. We will contact them to ask if they are still interested and available to participate in this AOB project. Based on the records that we collected from project 64623, we will be able to know which patient with autism have his parents as legal guardian or legal representative.

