**For aim 5:**

*The primary outcome measure* consists of investigating the differences between treatment conditions in oxytocin plasma concentration in ASD. Samples of post-administration of IN-OT will be analyzed. We will conduct ANOVA repeated measures on the different OXT concentration in 4 treatment conditions.

*The secondary outcome measure* consists of studying the differences between baseline oxytocin concentration between healthy subjects and ASD. T-tests will be conducted to determine the difference between two groups.

In this protocol, we have thought of several exploratory or secondary aims that include to compare brain function and functional connectivity between healthy controls and patients with ASD in response to resting state, in response to social cues and in response to interactive social games. We will also investigate the differences in behavioral and physiological responses between ASD and healthy subjects. We will also investigate differences between these two groups (during placebo administration) in baseline plasma OXT concentration, metabolome and exposome and cytokines levels.

In our exploratory analysis, we suggested to study the different factors that could explain heterogeneity in ASD such as clinical dissociation (different kinds of social deficits), behavioral and genetic and epigenetic contribution. We will conduct separate correlation analysis for each of these aims with the severity of ASD and brain function differences with controls. It is also possible to conduct factor analysis to study which behavioral variable for instance best predict ASD severity in clinical and brain function. The same applies for the best predictors of target engagement. We believe that not all patients with ASD will benefit from IN-OT. Hence, we will study the genetic factors, epigenetic factors, clinical classifications and behavioral patterns in determining TEE-OXT or OXT-effects.

It is possible that we publish separately target engagement results (comparison between doses of OXT) and oxytocin effects (24 and 48 as compared to placebo) on the same tasks that are conducted inside the MRI scanner.

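### Group II controls are recruited from a new source after patient testing has ended and counted with returning controls, and the plan uses neither source nor date in the secondary and exploratory ASD-versus-control comparisons

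*Combined protocol and SAP*

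**What the plan says.** **Patients.** The section on screening and recruitment draws them from protocol 64623: "We are recruiting participants who have previously participated in another study". No general-population route is described for ASD.

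**Original controls.** They come from the same place: "We will select healthy participants who already participated in our previous research study (64623".

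**New controls.** Because returning controls proved hard to bring back, "we need to recruit new people from general population in Atlanta", by flyer. The same section says of the patients "We have already conducted the total number of patients for this study", gives their IQ and race figures, and sets the new criteria from them: "another inclusion criterion for this separate group of healthy subjects (labeled II"). Those criteria are Caucasian race and IQ 70 to 115; they apply to group II only.

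**One control sample.** Two or three returning African American contacts are weighed against a single total: "This will make approximately 10% of the healthy subject's sample if we were able to recruit 30 total".

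**Analysis.** For baseline oxytocin (aim 5 in the statistical section, aim 4 in the objectives): "T-tests will be conducted to determine the difference between two groups". The imaging, behavioural and physiological comparisons with controls are listed there as exploratory or secondary, with no test named. The visit-order and time covariates under aims 1 to 3 belong to the treatment comparisons within ASD. The statistical section closes with a general promise to check confounders and to add analysis detail by amendment; it names neither source nor period.

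**The concern.** Matching on age, IQ and race does not balance when a person was scanned, how long the plasma was frozen, or whether he had already been through this research programme. For group II all three can differ systematically from the patients:

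- **Period.** Group II is enrolled after the last patient, so drift in scanner, staff or procedure falls on one side of the comparison.
- **Plasma.** Under Storage, plasma stays at -80°C until it is sent for analysis. If all samples are assayed together, storage time differs between patients and group II; if they are assayed as they accrue, assay batch differs.
- **Source.** Patients and returning controls have taken part in 64623, and the present task derives from it: "Participants will also perform a social ball game (adapted version from our previous project IRB00064623"). Group II has no such history.

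In a pooled two-group comparison these influences cannot be told apart from diagnosis. At stake are the baseline oxytocin comparison, a named secondary outcome with a predicted direction (lower in ASD), and the resting-state and task comparisons with controls.

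**Working it through.** **1. Does the confounding follow from the text?**

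| | ASD | Returning controls | Group II |
|---|---|---|---|
| Source | 64623 | 64623 | General population |
| Period | Testing complete | Some tested or to be tested late | After ASD testing |
| Added race and IQ limits | No | No | Yes |

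No patient shares group II's source or period. A source term in a model would not solve this: with no ASD patient in the new source, the adjusted ASD contrast rests on the returning controls alone.

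**2. The plan's own figure.** Statistical analysis says the planned numbers (50 ASD and 30 controls, from Participant selection) reliably detect d = 0.2 between groups, where 'reliably' is used elsewhere in that section to mean 95% power. For a two-sided t-test at 0.05 (alpha is not stated, so assumed), the noncentrality is 0.2 × √(50×30/80) = 0.2 × 4.330 = 0.866, and power is 13.7%. The figure is not reproduced. The confounding point does not depend on it, but it shows the effect size the plan has in mind.

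**3. Size of bias, under assumptions.** Bias in the pooled difference = (group II controls / 30) × shift. The documents give neither term. Assumed: 15 to 27 new controls out of 30, and a shift of 0.2 to 0.5 SD.

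- Low end: 15/30 × 0.2 = 0.10 SD
- Middle: 20/30 × 0.3 = 0.20 SD
- High end: 27/30 × 0.5 = 0.45 SD

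**4. False-positive rate with no true ASD effect.** Noncentral t, two-sided 0.05, noncentrality = bias × √(n₁n₂/(n₁+n₂)).

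| Bias (SD) | 50 v 30 | 30 v 30 |
|---|---|---|
| 0.10 | 7.1% | 6.7% |
| 0.20 | 13.7% | 11.9% |
| 0.45 | 48.6% | 40.3% |

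Simulation of the mixed control group (100,000 runs per setting) gives 7.1%, 13.6% and 47.9% for 50 v 30. The 30 v 30 column uses the minimum ASD number that the plan expects.

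**5. What the returning controls alone can show.** With 50 patients, two-sided 0.05:

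| Returning controls | Detectable d, 80% power | Power at d = 0.5 |
|---|---|---|
| 20 | 0.75 | 46% |
| 15 | 0.84 | 39% |
| 10 | 0.99 | 29% |
| 3 | 1.70 | 13% |

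All 30 controls would give a detectable d of 0.66. The returning-only comparison is useful as a sensitivity estimate, but too weak to serve as a significance test of whether an effect is real.

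**The case against.** **The trial's main conclusions are safe.** Every primary outcome compares 8 IU, 24 IU, 48 IU and placebo within patients, and no control enters it. This stands. A reader might infer that the dose findings are compromised; they are not.

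**The t-test sentence is narrow.** It covers baseline oxytocin. A reader might infer that every ASD-versus-control comparison will be a pooled, unadjusted t-test. The plan names no test for the others; pooling there is an inference from the single sample of 30.

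**The plan labels group II.** A reader might say that the plan throws the distinction away. It does not: the group has its own label, consent and criteria, so source is identifiable. What is missing is any stated use of it. The general confounder check does not supply that use.

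**Returning controls are not a clean reference.** This also stands. Some were still only interested in taking part when patient testing was complete, so they share the late period. Group II alone is restricted by race and IQ, so a difference between the control groups mixes those criteria with source and period. Patients also have a habituation scan and repeated visits, whereas every control has one scanning visit, so familiarity differs for returning controls too.

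**The magnitude is assumed.** Correct. The 10% remark does not show that 27 of 30 controls are new: it concerns only the African American contacts, and the 'mid-way' wording suggests that other returning controls had already been tested. Nor do the documents show that the scanner or procedures changed; the plan simply makes no provision to detect it.

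**Conclusion.** The point holds for the secondary and exploratory ASD-versus-control comparisons. By design, group II differs from the patients in period, recruitment source, and storage time or assay batch, and the plan uses neither source nor date. The direction of any bias is unknown. Its size rests wholly on assumption: 0.10 to 0.45 SD would raise the type I error to about 7% to 49% with 50 v 30. The low end is modest; the high end needs both a 90% share of new controls and a 0.5 SD shift. The range nevertheless brackets the d = 0.2 that the plan says it can detect. It would go too far to rule that a difference seen only against group II is not due to autism: with 10 to 20 returning controls, a real effect of d = 0.5 would be missed more often than found.

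**What to change.** 1. Carry control source (returning or group II) and the scan and blood-draw dates into the analysis dataset.
2. For each ASD-versus-control result, report with confidence intervals the pooled difference, the returning-controls-only difference as a sensitivity analysis, and a direct returning-versus-group II comparison. Note that the last also reflects the race and IQ criteria.
3. State that source cannot be fully adjusted for, because no patient was newly recruited, and read the pooled differences with that caution. Do not base a rule on significance against one control subgroup.
4. Assay any plasma not yet assayed with ASD and control samples interleaved in the same batches, and report storage time by group. Interleaving deals with batch, not with storage time, which is why both are needed.

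The cost is two or three variables, some extra rows per comparison and an assay-order instruction, with no new participants or visits. The returning-only intervals will be wide and should be presented as such. The plan already expects further analysis detail by amendment, so this can go in there.
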